### 9.2 SECONDARY ENDPOINTS

#### 9.2.1 Secondary efficacy endpoints (6-month core period)

##### ***9.2.1.1 Values at each assessment visit and changes from baseline for the total RAID score, HADS, MATHys, FACIT-Fatigue, HAQ-DI, morning stiffness, International Physical Activity Questionnaire, and patient global assessment of disease activity***

All the studied PROs will be assessed at each visit over the treatment period (from V2 to V5). Questionnaires used are all valid and self-rating reliable scales.

The **Hospital Anxiety and Depression Scale (HADS)** measures anxiety and depression in both hospital and community settings. This questionnaire comprises 14 items divided into two subscales: anxiety and depression (see Appendix B). Each item is answered by a 0 to 3 rating scale, leading to maximum scores of 21 points for anxiety and depression. A total score up to 19 indicates a major depressive episode; a total score up to 13 indicates adjustment disorders and minor depression.

The **Multidimensional Assessment of Thymic States (MATHys)** is a multi-dimensional assisted self-administered questionnaire comprising five dimensions (emotional reactivity, cognition speed, psychomotor function, motivation and sensory perception) divided into 20 items relating to individual states as perceived by patients for the preceding week (see Appendix B). Each item is set out as a continuous measure in the form of a visual analogic scale of 10 cm on which the subject is asked to make a mark to indicate where he/she is positioned between the two predefined extreme propositions.

The **Functional Assessment of Chronic Illness Therapy – Fatigue (FACIT-F)** is a symptom-specific scale that measures fatigue in patients assess with chronic illness therapy over the 7 preceding days. This scale comprises 13 items scored on a 5-point Likert scale, from 0 (not at all) to 4 (very much) (see Appendix B). The figures are reversed during score calculations, so that higher score values indicate more favorable conditions. Total scores then range from 0 to 52, with lower scores representing greater fatigue.

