**APPENDIX**

**FACIT-Fatigue (Functional Assessment of Chronic Illness Therapy – Fatigue) – Version 4**

Below is a list of statements that other people with your illness have said are important. Please circle or mark one number per line to indicate your response as it applies to the **past 7 days**.

		Not at all	A little bit	Some- what	Quite a bit	Very much
HI7	I feel fatigued .....	0	1	2	3	4
HI12	I feel weak all over .....	0	1	2	3	4
An1	I feel listless (“washed out”) .....	0	1	2	3	4
An2	I feel tired.....	0	1	2	3	4
An3	I have trouble starting things because I am tired.....	0	1	2	3	4
An4	I have trouble finishing things because I am tired .....	0	1	2	3	4
An5	I have energy.....	0	1	2	3	4
An7	I am able to do my usual activities.....	0	1	2	3	4
An8	I need to sleep during the day .....	0	1	2	3	4
An12	I am too tired to eat.....	0	1	2	3	4
An14	I need help doing my usual activities .....	0	1	2	3	4
An15	I am frustrated by being too tired to do the things I want to do .....	0	1	2	3	4
An16	I have to limit my social activity because I am tired.....	0	1	2	3	4

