5.1.5.3. To explore patients' profiles

Patients' profiles will be explored using the same analyses performed for the analysis of baseline data. Association between cognitive troubles and patients' characteristics will be tested. Cognitive troubles will be evaluated by the MATHyS cognition score as qualitative variable (using the tertiles: <1st tertile, [1st tertile; 2nd tertile[, ≥ 2nd tertile).

Characteristics (at baseline) to be tested are:

- Age in quantitative or in classes (using quartiles) if linearity is not verified
- Sex (Female / Male)
- BMI in classes (Normal/Abnormal i.e Underweight or Overweight or Obese)
- Time between baseline and initial diagnosis (years) in quantitative or in classes (using quartiles), if linearity is not verified
- DAS28-ESR in quantitative or in classes (using quartiles), if linearity is not verified
- Patient previously treated with biological therapies and targeted synthetic DMARDs (Yes/No)
- Patient currently treated with corticosteroids for his/her RA (Yes/No)
- Patient currently treated with NSAIDs, analgesics (Yes/No)
- Patient having experienced any past or concomitant diseases (clinically significant) (Yes/No)
- Depression evaluated by HADS (Yes/No). If HADS depression = 'Normal' then Depression='No'. Else if HADS depression = 'Boderline abnormal' or 'Abnormal' then Depression='Yes'
- Anxiety evaluated by HADS (Yes/No). If HADS anxiety = 'Normal' then Anxiety='No'. Else if HADS anxiety = 'Boderline abnormal' or 'Abnormal' then Anxiety='Yes'
- Fatigue (FACIT-F total score) in quantitative or in classes (using quartiles), if linearity is not verified
- Global Assessment of disease activity (mm) by patient (0-no pain to 100-maxima pain imaginable) in quantitative or in classes (using quartiles), if linearity is not verified
- Global Assessment of disease activity (mm) by physician (0-no pain to 100-maxima pain imaginable) in quantitative or in classes (using quartiles), if linearity is not verified
- MATHyS global score in quantitative (only descriptive, not in the model due to collinearity with cognition score)
- Positive Anti-CCP (Yes/No)
- Positive rheumatoid factor (Yes/No)

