5.3.2.3. Secondary efficacy analyses

For each of the secondary endpoints, values at each assessment visit over the treatment period and changes from baseline for each PROs questionnaires total score to evaluate the RA activity will be presented (absolute and relative variation). 95% CI will be provided.

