8.3. VALIDATION OF PROGRAMS

Validations will be done according to the procedure of the CRO ITEC Services.

The program reviewer is responsible for reviewing each project program and output provided to the sponsor. Program logs are reviewed for logical, syntax and fatal errors. The review in SAS® includes, but is not limited to, all ERRORS, WARNINGS, BY-VALUE merge messages, NOTES, and UNINITIALIZED variables. Program logs are also reviewed for accurate and consistent variable and observation counts following each procedure and data step.

The reviewing statistician is responsible for checking and reviewing the work produced using whatever method he/she feels is appropriate (e.g., SAS® code review, hand calculation, etc.) to reassure of the quality of the output.

Outputs are reviewed for typographical errors, misspellings and nonsensical values or results and to check the consistency with the statistical and analysis plan. Outputs are cross-checked against each other for accuracy and consistency. For statistical tables, listings, appendix listings, and figures, this procedure includes comparison of subject group numbers, counts of subjects at each observation point, and consistency of results for variables between outputs.

Findings of the quality control reviews are communicated to the party responsible for making necessary changes. The programs will be retested after modifications.

After final review, and when no further changes are required to produce the deliverable, the program reviewer and the statistician in charge of the study need to complete and sign a validation checklist, to indicate that they have successfully performed all of their responsibilities.

Copies of the internal quality control forms produced for the validation process and the sign-off forms will be provided to the sponsor to support the validation if asked.

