APPENDIX A: DERIVED DATA

The derived data are variables which are calculated from the raw data in the CRF/eCRF and not included in the database (e.g.: AUC, total score, duration, summary value from repeated observations, study exposure, study drug exposure, study drug cumulative dose, etc.).

The formula used for derived data should be provided and examples may be necessary to clarify the calculation. The strategy for missing data must be specified in the calculation of derived data (e.g.: the minimum number of observations required to calculate an average score, handling incomplete dates).

All references used to calculate the derived data should be mentioned below.

The following derived data will be calculated and included in the listings:

(1) SUBGROUPS DECISION

Treatment started before screening visit and ongoing at screening visit	Prescribed treatment at baseline
csDMARDs	Sarilumab + csDMARDs
Biological therapy	Sarilumab + csDMARDs
csDMARDs or biological therapy	Sarilumab in monotherapy

(2) DAS28-ESR

$DAS28-ESR = 0.56 \times \sqrt{TJC28} + 0.28 \times \sqrt{SJC28} + \ln(ESR) + 0.014 \times PtGA$ (in mm)

Where:

- ln is the natural logarithm
- SJC is the swollen joints
- TJC is the tender joints
- PtGA is the patient's global assessment of disease activity (using a 100 mm VAS)
- ESR is the erythrocyte sedimentation rate (mm/h)

(3) CDAI

$CDAI = TJC28 + SJC28 + PtGA(\text{in cm}) + PhGA(\text{in cm})$

Where:

- SJC is the swollen joints
- TJC is the tender joints
- PhGA is the physician's global assessment of disease activity (using a 100 mm VAS)
- PtGA is the patient's global assessment of disease activity (using a 100 mm VAS)

(4) BMI

BMI (kg/m²) will be derived as $\text{Weight (kg)} / [\text{Height (cm)} / 100]^2$ and rounded to the nearest decimal.

(5) Time between baseline and initial diagnosis (years)

Time between baseline and initial diagnosis in years will be calculated as $(\text{initial diagnosis date} - \text{baseline visit date} + 1) / 365.25$.

(6) Changes from baseline (V2)

Absolute variation (points) from baseline will be calculated as a difference from baseline (e.g. assessment at the visit – assessment at baseline).

Relative variation (%) from baseline will be calculated as: $((\text{assessment at the visit} - \text{assessment at baseline}) / \text{assessment at baseline}) * 100$.

If necessary, evolution will be presented according to decision tables from Appendix B.

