(14) **Hospital Anxiety Scale (issue from HADS)**

Total score of anxiety is the sum of tick boxes of columns A (see Appendix D). The range of the total score of anxiety value is 0-21.

(15) **Multidimensional Assessment of Thymic States (MATHys):**

The MATHys is a visual analog scale consisting of 20 items varying from 0 to 10 (see Appendix H). These items corresponded to five dimensions: emotional, cognition, psychomotor function, motivation and sensory perception.

Total score is the sum of the 20 items. The measure is the number of centimetres from the left hand anchor. Items measured from 0 to 10 are: 1; 2; 3; 4; 11; 12; 13; 14; 15; 16; 19; 20 and items measured from 10 to 0 are : 5; 6; 7; 8; 9; 10; 17; 18. A score of 0 corresponds to inhibition of the state evaluated by the item. A score of 5 indicates no change from the patient's usual state and a score of 10 corresponds to excitation for the evaluated state. An overall score of between 0 and 200 is thus obtained. This scale is not devoted to make a diagnosis of mood state but allow to determine the general level of inhibition/activation processes (lower scores indicate general inhibition and higher scores indicate general excitation).

The subscore for **emotional** is obtained by the sum of items: 3; 7; 10; 18. This range is 0 (hyporeactive)-40 (hyperreactive).

The subscore for **cognition** is obtained by the sum of items: 5; 9; 12; 14. This range is 0 (Retardation)-40 (Acceleration).

The subscore for **psychomotor function** is obtained by the sum of items: 2; 11; 19. This range is 0 (Retardation)-30 (Acceleration).

The subscore for **motivation** is obtained by the sum of items: 4; 15; 16; 17. This range is 0 (Decrease)-40 (Increase).

The subscore for **sensory perception** is obtained by the sum of items: 1; 6; 8; 13; 20. This range is 0 (Decrease)-50 (Increase).

See: Chantal Henry, Katia M'Bailara, Flavie Mathieu, Rollon Poinot, Bruno Falissard Construction and validation of a dimensional scale exploring mood disorders: MATHys (Multidimensional Assessment of Thymic States). BMC Psychiatry. 2008; 8: 82.

(16) **Functional Assessment of Chronic Illness Therapy – Fatigue (FACIT-F) per item and total score**

The FACIT measurement system is a comprehensive compilation of questions that measure health related QOL in patients with chronic illnesses. The FACIT-F includes the 13 items.

FACIT-F score is the sum of items, this range is 0 to 52. High FACIT-F scores represent less fatigue.

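### SAP Appendix A (16) scores FACIT-Fatigue as a plain sum of items, which on the printed form runs opposite to the direction the SAP states

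*SAP*

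**What the plan says.** SAP Appendix A, item (16), defines the FACIT-F total in one sentence and gives its direction in the next: "FACIT-F score is the sum of items, this range is 0 to 52. High FACIT-F scores represent less fatigue". It describes no reversal step and names no items to reverse.

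Protocol 9.2.1.1 gives the same 0–52 range and the same direction, and it does call for reversal: "The figures are reversed during score calculations, so that higher score values indicate more favorable conditions". It does not say which items are reversed. SAP 1.6, which lists modifications from the protocol, does not mention FACIT-F scoring.

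The form in Protocol Appendix B codes every item from 0 (not at all) to 4 (very much). Eleven items (HI7, HI12, An1, An2, An3, An4, An8, An12, An14, An15, An16) describe fatigue or its consequences. Two do not: An5, about having energy, and An7, "I am able to do my usual activities".

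The introduction to SAP Appendix A sets its own standard for derived variables: "The formula used for derived data should be provided and examples may be necessary to clarify the calculation". Item (15), on MATHyS, meets that standard by listing its reversed items: "items measured from 10 to 0 are : 5; 6; 7; 8; 9; 10; 17; 18". Item (16) has no such list.

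The FACIT-F total is a secondary endpoint (SAP 5.1.3). Under SAP 5.3.2.3, changes in the questionnaire totals "will be presented (absolute and relative variation", that is, in points and in per cent. The total also enters the exploratory profile analyses as a candidate factor: "Fatigue (FACIT-F total score) in quantitative or in classes (using quartiles), if linearity is not verified".

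**The concern.** The SAP is the document a programmer works from. Followed literally, item (16) produces a total that rises with fatigue, while the label attached to it says that high values mean less fatigue. A patient whose fatigue lessens would usually be reported as worsening. In the profile model, the association between fatigue and the MATHyS cognition classes would be read the wrong way round.

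Going back to the protocol does not fully settle the rule, because its reversal sentence names no items. The scoring of a named patient-reported endpoint should not have to be inferred, least of all in a trial whose purpose is patient-reported outcomes.

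**Working it through.** **Inputs.** There are 13 items, each marked 0 to 4 (Protocol 9.2.1.1 and the form in Protocol Appendix B). Let S be the sum of the 11 fatigue-worded items as marked (0 to 11 × 4 = 44). Let q = An5 + An7 as marked (0 to 2 × 4 = 8).

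**The stated range.** 13 × 0 = 0 and 13 × 4 = 52, so the 0–52 range is arithmetically right. It cannot show whether the scoring is right, because any mix of reversed and unreversed items has the same arithmetic limits. The test is whether the least and most fatigued patients land on the correct ends.

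**Three possible rules.**

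- Plain sum, as SAP (16) is written: S + q
- All 13 items reversed: (44 − S) + (8 − q) = 52 − S − q
- Eleven reversed, An5 and An7 kept: (44 − S) + q

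| Patient | S | q | Plain sum | All 13 reversed | 11 reversed, 2 kept |
|---|---|---|---|---|---|
| No fatigue | 0 | 8 | 8 | 44 | 52 |
| Maximal fatigue | 44 | 0 | 44 | 8 | 0 |

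Only the last column gives 52 to the least fatigued patient and 0 to the most fatigued, so only that rule matches both the range and the direction in the two documents.

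**Error of the plain sum.** Plain minus correct = (S + q) − (44 − S + q) = 2S − 44. The error in a change score is therefore 2 × (change in S), which is negative whenever the fatigue items improve.

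**Illustrations (assumed patients, each improving one category on every item; not estimates of bias in this trial).**

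- From the mid-point, S 22 to 11 and q 4 to 6. Correct: 26 to 39, +13 (+50.0%). Plain sum: 26 to 17, −9 (−34.6%). The difference is −22 = 2 × (−11).
- From a worse start, S 33 to 22 and q 2 to 4. Correct: 13 to 26, +13 (+100%). Plain sum: 35 to 26, −9 (−25.7%).

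Read with the SAP's label, both improvements would be reported as worsening.

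**If the protocol sentence were read as reversing all 13.** Reverse-all minus correct = (52 − S − q) − (44 − S + q) = 8 − 2q, which lies between −8 and +8. The error in change is −2 × (change in q): zero if An5 and An7 do not move, and 4 points too low if each improves by one category. In the mid-point case this rule gives 26 to 35, +9 (+34.6%), instead of +13.

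**The case against.** The strongest reply is that the intent is clear. The protocol requires reversal, both documents state the range and direction, and the item wording then leaves one sensible rule. SAP 1.6 announces no change, and item (16) cites a validation paper for the scale in rheumatoid arthritis. SAP 8.3 provides for code review and hand calculation as well as an output check: "Outputs are reviewed for typographical errors, misspellings and nonsensical values or results". FACIT-F is also reported item by item, so a miscoded total could be traced and corrected. All of this supports reading the gap as an omission and limits its weight. It does not put the formula in the SAP, and the one rule that is there gives the wrong direction.

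Two points cannot be excluded. If the database stores item values already reversed, a plain sum is correct; no readable text says so, and Appendix A describes derived data as calculated from the raw case report form data. The copy of the form in SAP Appendix E is not legible in the public text, so the check uses the protocol's form, and a scoring note in the SAP copy is possible.

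A reader might infer more than the documents support:

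- **That the plan prescribes reversing all 13 items and will understate improvement.** The SAP prescribes no reversal. The protocol sentence gives its purpose as making higher values favourable, which reversing An5 and An7 would defeat. Reverse-all is a possible misreading to guard against. Whether validation would catch it is conjecture.
- **That IPAQ cannot be scored as planned.** Item (18) does contain a paragraph denying domain-specific estimates, which conflicts with the per-domain results in SAP 5.1.3. But that paragraph is expressly about the short form, which this trial does not use. Item (18) opens by listing the domains, cites the IPAQ guidelines, and its day criteria refer to any combination of activities, which favours adding days across items. The remaining questions, such as how several items combine and what weight transport cycling takes, are missing detail rather than a wrong rule.

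**Conclusion.** The point holds for FACIT-F. As written, SAP Appendix A (16) gives 8 for no fatigue and 44 for maximal fatigue, against its own statement that high scores mean less fatigue, and it omits the reversal that the protocol requires. The correct endpoints, 52 and 0, follow from the documents' own range, direction and item wording, with no outside source. The conclusion assumes that item values are stored as marked on the protocol's form.

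The consequence is bounded. FACIT-F is one of several secondary patient-reported endpoints, Protocol 11.4.2.3 treats the analyses as descriptive, and the total is one of many candidate factors in an exploratory model. The primary RAID analysis is unaffected. SAP 1.6 says a baseline-data analysis has already been performed, and SAP 5.1.5.3 repeats its profile analyses with FACIT-F as a candidate factor. The separate plan for that analysis is not available here, so whether its scoring was right is unknown.

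For IPAQ, what stands is one surplus paragraph that contradicts a planned output.

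**What to change.** In SAP Appendix A (16), state that HI7, HI12, An1, An2, An3, An4, An8, An12, An14, An15 and An16 are each scored 4 − x, that An5 and An7 are kept as marked, and that the 13 values are summed, so that 52 is no fatigue and 0 is maximal fatigue. First confirm whether the database holds values as marked. If it already stores reversed values, say so instead, and confirm that An5 and An7 were left unreversed. The two extreme patients in the table above would serve as the worked example that the Appendix A introduction allows for.

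Then check the scoring program against those two cases, and check how FACIT-F was scored in the baseline-data analysis. Rerun the affected baseline output if it was wrong.

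As clean-up, delete the short-form paragraph from item (18).

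The cost is a few lines of SAP text, a program check and a look back at the baseline output. No new data are needed, and no protocol amendment, since the protocol already requires reversal.

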The **Stanford Health Assessment Questionnaire Disability Index (HAQ-DI)** is a patient-oriented outcome assessment questionnaire specifically developed to assess the extent of a RA patient's functional ability. It consists of 20 questions referring to eight component sets: dressing/grooming, arising, eating, walking, hygiene, reach, grip, and activities (see Appendix B). Knowing that here are 2 or 3 questions for each section, scoring within each section is from 0 (without any difficulty) to 3 (unable to do). The eight category scores are averaged into an overall HAQ-DI score on a scale from zero (no disability) to three (completely disabled). It is not truly continuous but has 25 possible values.

The **duration of morning stiffness** (in minutes) will be self-reported by RA patients.

The **International Physical Activity Questionnaire (IPAQ)** is a 27-item self-reported questionnaire designed to measure physical activity of patient. It comprises several parts (job-related, transport-related, domestic and leisure-time physical activity) and intensities (moderate, vigorous, walking) and includes sitting time (see Appendix B). Based on frequency, duration and intensity of self-reported physical activity, individuals are categorized into low, moderate and high physical activity groups.

The **patient global assessment of disease activity** measures RA activity as perceived by the patient, using a 100 mm horizontal visual analog scale (VAS).

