6.3. DATA HANDLING CONVENTIONS FOR PATIENT REPORTED OUTCOMES

The management of missing data for PRO is described in [Appendix A](#).

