(7) Duration of IMP exposure (week)

The duration of IMP exposure is defined as follows: $(\text{last dose date} - \text{first dose date} + 14 \text{ days}) / 7$ regardless of unplanned intermittent discontinuations.

(8) Enrollment duration (months)

Enrollment duration (months) will be calculated as: $((\text{date of last patient last visit} - \text{date of first patient first visit}) + 1) / 30.4375$.

(9) Follow-up duration (weeks)

Follow-up duration in weeks will be calculated as: $((\text{date of last contact with the patient} - \text{date of baseline}) + 1) / 7$.

(10) Time between baseline and premature withdrawal (weeks)

Time between baseline and premature withdrawal in weeks will be calculated as $((\text{withdrawal date} - \text{baseline visit date}) + 1) / 7$.

(11) Time between measures of the rheumatoid nodule (months)

Time between measures of the rheumatoid nodule (months) will be calculated as: $(\text{date of the last measure of the rheumatoid nodule} - \text{date of screening}) + 1) / 30.4375$.

(12) RAID

The RAID is calculated based on 7 Numerical rating scales (NRS) questions (see Appendix C). Each NRS is assessed as a number between 0 and 10. The 7 NRS correspond to pain, function, fatigue, sleep, emotional well-being, physical well-being, and coping/self-efficacy.

Calculation: RAID final value = $(\text{pain NRS value (range 0-10)} \times 0.21) + (\text{function NRS value (range 0-10)} \times 0.16) + (\text{fatigue NRS value (range 0-10)} \times 0.15) + (\text{phys well being NRS value (range 0- 10)} \times 0.12) + (\text{sleep NRS value (range 0-10)} \times 0.12) + (\text{emotional well being NRS value (range 0-10)} \times 0.12) + (\text{coping NRS value (range 0-10)} \times 0.12)$.

Thus, the range of the final RAID value is 0-10 where higher figures indicate worse status. Missing data imputation: If one of the 7 NRS values composing the RAID is missing, the imputation is as follows:

- a. calculate the mean value of the 6 other (non-missing) NRS (range, 0-10)
- b. impute this value for the missing NRS
- c. Then, calculate the RAID as explained above. If 2 or more of the NRS are missing, the RAID is considered as missing value (no imputation).

See: http://pitie-salpetriere.aphp.fr/psaid/raid_psaidd_quest_home.php

(13) **Hospital Depression Scale (issue from HADS)**

Total score of depression is the sum of tick boxes of columns D (see Appendix D). The range of the total score of depression value is 0-21.

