See: CELLA, D, YOUNT, S, SORENSEN, M, CHARTASH, E, SENGUPTA, N ET GROBER, J. Validation of the Functional Assessment of Chronic Illness Therapy Fatigue Scale relative to other instrumentation in patients with rheumatoid arthritis. *J Rheumatol.* 2005; 32: 811-9.

(17) **The Health Assessment Questionnaire - Disability Index (HAQ-DI)**

There are 8 sections: dressing, arising, eating, walking, hygiene, reach, grip, and activities. There are 2 or 3 questions for each section. Scoring within each section is from 0 (without any difficulty) to 3 (unable to do). For each section the score given to that section is the worst score within the section, i.e. if one question is scored 1 and another 2, then the score for the section is 2. In addition, if an aide or device is used or if help is required from another individual, then the minimum score for that section is 2. If the section score is already 2 or more then no modification is made.

The 8 scores of the 8 sections are summed and divided by 8. The result is the disability index. In the event that one section is not completed by a subject then the summed score would be divided by 7. In the event that two section is not completed by a subject then the summed score would be divided by 6 etc. The score range is 0 to 3.

See: Bruce, Bonnie, et James F Fries. « The Stanford Health Assessment Questionnaire: Dimensions and Practical Applications ». *Health and Quality of Life Outcomes* 1, n° 1 (2003): 20. <https://doi.org/10.1186/1477-7525-1-20>.

(18) **International Physical Activity Questionnaire (IPAQ)**

IPAQ assesses physical activity undertaken across a comprehensive set of domains including: leisure time physical activity, domestic and gardening (yard) activities, work-related physical activity and transport-related physical activity.

Results can be reported in categories (low activity levels, moderate activity levels or high activity levels) or as a continuous variable (MET minutes a week). MET minutes represent the amount of energy expended carrying out physical activity. A MET is a multiple of your estimated resting energy expenditure. One MET is what you expend when you are at rest. To get a continuous variable score from the IPAQ (MET minutes a week) we will consider walking to be 3.3 METS, moderate physical activity to be 4 METS and vigorous physical activity to be 8 METS.

Walking MET-minutes/week = 3.3 * walking minutes * walking days

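### SAP Appendix A (17) sets no minimum number of answered sections for HAQ-DI, so very incomplete forms can give unreliable individual changes from baseline

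*SAP*

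**What the plan says.** SAP 6.3 sends the reader to one place for incomplete questionnaires: "The management of missing data for PRO is described in" Appendix A. The introduction to Appendix A says that the missing-data strategy has to be given with each derived variable, and its first example is the minimum number of observations needed for an average score.

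The scores then differ in how far they follow this:

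- **HAQ-DI, Appendix A (17).** For a full form, "The 8 scores of the 8 sections are summed and divided by 8". With one section missing the divisor is 7. After that, "In the event that two section is not completed by a subject then the summed score would be divided by 6 etc". No minimum is given.
- **RAID, Appendix A (12).** One missing item is replaced by the mean of the other six. Beyond that, "If 2 or more of the NRS are missing, the RAID is considered as missing value (no imputation".
- **HADS, Appendix A (13) and (14).** "Total score of depression is the sum of tick boxes of columns D" and "Total score of anxiety is the sum of tick boxes of columns A". Nothing is said about unticked items.
- **MATHyS, Appendix A (15).** "Total score is the sum of the 20 items". Nothing is said about unmarked items.
- **FACIT-F, Appendix A (16).** Also a plain sum, with no rule for blanks.
- **IPAQ, Appendix A (18).** Cases with missing time or days are removed.

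SAP 6.4 adds that, outside discontinuation for lack of efficacy or adverse events, missing data are not replaced. Protocol 9.2.1.1 describes HAQ-DI as the average of eight category scores and notes: "It is not truly continuous but has 25 possible values".

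**The concern.** HAQ-DI is an average, the kind of score for which the SAP's own introduction gives a minimum as an example of what to specify. Without one, a form with one or two answered sections counts the same as a complete form. SAP 5.3.2.3 reports absolute and relative change from baseline at each visit. A patient who answers all eight sections at baseline and a few at Week 24 is then compared across different sets of activities, and the difference is recorded as change even if function has not altered.

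At stake are the HAQ-DI values and changes, a secondary endpoint of the core period. For the sum scores the problem is that the rule is unwritten. A program that adds whatever was answered and a program that requires every item give different results from the same data, and the SAP does not say which to use.

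**Working it through.** **Inputs.** The HAQ-DI scoring rule (eight sections, each 0 to 3) is from SAP Appendix A (17), and the count of 25 possible values is from Protocol 9.2.1.1. For scale, Protocol 4.1.2 quotes mean HAQ changes on sarilumab 200 mg of -0.55 (MOBILITY, week 16), -0.47 (TARGET, week 12) and -0.61 (MONARCH, week 24). Neither document gives section profiles or a rate of incomplete forms, so the two profiles below are assumptions, chosen to show a range.

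**Step 1: reproduce the plan's figure.** Eight sections scored 0 to 3 give sums 0 to 24. Divided by 8, that is 25 values, as the protocol states. If any number of sections from 1 to 8 is accepted, sum/k takes 67 distinct values.

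**Step 2: largest false change.** Let one visit be complete and the other have k sections answered, with no real change. The error is (mean of the k answered sections) minus (mean of all 8). Both profiles have a true score of 12/8 = 1.50.

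- Spread profile 3,3,2,2,1,1,0,0, the two highest skipped: (12 - 6)/6 = 1.00, error -0.50.
- Same profile, the four highest skipped: (1+1+0+0)/4 = 0.50, error -1.00.
- Same profile, only the two zeros answered: 0/2 = 0, error -1.50.
- Flat profile 2,2,2,2,1,1,1,1, two of the 2s skipped: (12 - 4)/6 = 1.33, error -0.17.
- Same profile, all four 2s skipped: 4/4 = 1.00, error -0.50.

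The errors are symmetric: skipping the easiest sections gives the same size with a plus sign.

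**Step 3: skipping at random.** Over all subsets of size k the mean error is 0.00. The standard deviation is s × √[(8 - k)/(7k)], where s is the SD of the eight section scores (divisor 8): √1.25 = 1.118 for the spread profile and 0.50 for the flat one. For example, spread with k = 6: 1.118 × √(2/42) = 0.24.

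| Sections answered | Spread: largest error | Spread: SD if random | Flat: largest error | Flat: SD if random |
|---|---|---|---|---|
| 7 | ±0.21 | 0.16 | ±0.07 | 0.07 |
| 6 | ±0.50 | 0.24 | ±0.17 | 0.11 |
| 5 | ±0.70 | 0.33 | ±0.30 | 0.15 |
| 4 | ±1.00 | 0.42 | ±0.50 | 0.19 |
| 3 | ±1.17 | 0.55 | ±0.50 | 0.24 |
| 2 | ±1.50 | 0.73 | ±0.50 | 0.33 |
| 1 | ±1.50 | 1.12 | ±0.50 | 0.50 |

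**Step 4: effect of a floor.** With a minimum of six sections, the largest error falls from 1.50 to 0.50 (spread) and from 0.50 to 0.17 (flat). If both visits are incomplete the two errors can add, with or without a floor.

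**Step 5: effect on the group mean.** One patient with a false change of -1.00 among the 112 evaluable patients in the protocol synopsis moves the mean by 1.00/112 = 0.009.

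**Step 6: the sum scores, only if a blank were added as zero.** A HADS subscale score of 11 with an item worth 1 to 3 left blank would become 10 to 8. That moves it from Abnormal to Borderline, which Appendix B Figure 4 labels as improvement. For MATHyS even the sign is undetermined. The usual state is 5 per item, so a blank scored 0 lowers the total by 5. But eight of the 20 items are measured in reverse, and a raw 0 stored before reversal would score 10 and raise it by 5.

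**The case against.** Two stronger readings are tempting, and the documents support neither.

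A reader might infer that the HAQ-DI rule biases the trial's mean change, because patients skip what is hardest for them. Nothing in the protocol or SAP says so. The form gives a patient who cannot do a task an answer for it, and use of aids or help raises a section to at least 2. Under random skipping the mean error is zero, and Step 5 shows how little one extreme form moves the mean. Setting an individual change of -1.00 beside trial means of about -0.5 gives a sense of scale, no more.

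A reader might also infer that blank HADS or MATHyS items are scored as zero. No section says that. The principle in SAP 6.4 that missing data are not replaced fits at least as well with setting the score to missing, and a sum of 20 items is undefined when one is absent. What remains is an unwritten detail.

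Other points also stand. The 25 values describe a complete form and do not contradict a rule for incomplete ones. The RAID cut-off belongs to a different, weighted instrument. The spread profile is an extreme. Forms are completed at clinic visits, and exclusion E 02 removes patients unable to complete the PROs, so very incomplete forms may be few. The HAQ-DI rule cites an instrument paper that is not available here.

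None of this supplies the missing minimum.

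**Conclusion.** The HAQ-DI point holds as a minor defect: a stated rule without a lower limit, in an appendix whose introduction gives that limit as an example of what to specify. Its consequence is unreliable individual scores and changes. Under the two assumed profiles, with one complete form and no real change, the error can reach 0.17 to 0.50 with six sections answered, 0.50 to 1.00 with four, and 0.50 to 1.50 with one or two. Bias in the mean would need skipping related to difficulty, which is possible but not shown. The size of the effect in this trial cannot be computed, because no rate of incomplete forms is given.

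For HADS, MATHyS and FACIT-F the finding is only that the item-level rule is unstated. It has some reach: the MATHyS cognition score in tertiles is the outcome of the patient-profile analysis, HADS classes are among its predictors, and the factorial analysis drops any patient with a missing value.

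The primary RAID score has a complete rule and is unaffected. The scores concerned are secondary or exploratory, and Protocol 11.4.2.3 calls all analyses descriptive.

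**What to change.** In Appendix A (17), replace the open-ended divisor with a floor: compute HAQ-DI as the mean of the answered sections if at least 6 of 8 are answered, and set it to missing otherwise. Say what makes a section count as answered, and report the number of incomplete and excluded forms at each visit. The value of 6 is a proposal and does not come from the documents. A stricter floor would reduce the remaining error further and lose more forms.

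In Appendix A (13) to (16), state that blank items in HADS, MATHyS and FACIT-F are never summed as zero. Either set the score to missing, or prorate within the subscale above a stated minimum. If prorating is chosen, add a line to SAP 6.4 so that the two sections agree.

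The cost is a few lines of SAP text and code. The small downside is that very incomplete forms become missing.
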